Encephalitis (NCI-CTCAE v4.03)		
Grade	Recommended Adverse Event management guidelines	Mandatory Dose Modification requirements
Grade 1 (asymptomatic or mild symptoms)		Continue PDR001 treatment
Grade 2 (New onset of moderate)	
 Consider consulting neurology 0.5 to 1 mg/kg/day prednisone equivalents 	
1st occurrence:
 
 Interrupt PDR001 until recovery to ≤ Grade 1 or baseline.

Encephalitis (NCI-CTCAE v4.03)		
Grade	Recommended Adverse Event management guidelines	Mandatory Dose Modification requirements
symptoms, limiting instrumental ADL)		
 Once recovered restart PDR001 treatment at the same dose and schedule. 
AE resolution to ≤ Grade 1 or baseline must occur within a period of 12 weeks since Grade 2 event has been identified, otherwise PDR001 must be permanently discontinued.
 
If worsens, treat as Grade 3-4
 
2nd occurrence: Permanently discontinue PDR001

Grade 3 or 4 (New onset of severe symptoms, limiting self-care ADL, life-threatening)	
 Consider consulting neurology 1 to 2 mg/kg/day prednisone equivalents 	Permanently discontinue PDR001

Table 6-8 Mandatory dose modification requirements and recommended clinical management guidelines for potential immune-related endocrine events

Endocrine events (NCI-CTCAE v4.03)		
Grade	Recommended Adverse Event management guidelines	Mandatory Dose Modification requirements
Asymptomatic, intervention not indicated (e.g. hyperthyroidism or hypothyroidism)	
 If TSH <0.5x LLN, or TSH >2x ULN, or consistently out of range in 2 subsequent measurements, include free T4 at subsequent cycles as clinically indicated Consider endocrinologist consult If hypophysitis is considered, pituitary gland imaging should be considered (MRIs with gadolinium and selective cuts of the pituitary can show enlargement or heterogeneity and confirm the diagnosis) Repeat labs in 1 to 3 weeks/MRI in 1 month if laboratory abnormalities persist but normal lab/pituitary scan 	Continue PDR001 treatment
Symptomatic endocrinopathy (e.g., hypophysitis, adrenal insufficiency, hypothyroidism, hyperthyroidism)	
 Consider Endocrinology consultation Rule out infection and sepsis with appropriate cultures and imaging Treat with an initial dose of methylprednisolone 1 to 2 mg/kg intravenously followed by oral prednisone 1 to 2 mg/kg per day. Replacement of appropriate hormones may be required as the steroid dose is tapered Hypophysitis with clinically significant adrenal insufficiency and hypotension, dehydration, and electrolyte abnormalities (such as hyponatremia and hyperkalemia) constitutes adrenal crisis Consider hospitalization and intravenous methylprednisolone should be initiated. 	
1st occurrence:
 
 Interrupt PDR001 until symptomatic recovery to mild (e.g. grade 1) or no symptoms Once recovered, restart PDR001 treatment at the same dose and schedule 
AE resolution to mild or no symptoms must occur within a period of 12 weeks since symptomatic endocrinopathy event has been identified, otherwise PDR001 must be permanently discontinued.

Endocrine events (NCI-CTCAE v4.03)		
Grade	Recommended Adverse Event management guidelines	Mandatory Dose Modification requirements
		2 nd occurrence: Permanently discontinue PDR001
Autoimmune diabetes (Grade 3 or symptomatic hyperglycemia)	Initiate anti-glycemic therapy (i.e. insulin) as medically indicated and monitor glucose levels regularly until metabolic control is achieved	Interrupt treatment until glucose returns to Grade 1 or baseline and then restart PDR001
Autoimmune diabetes (Grade 4 hyperglycemia or life-threatening complications)	Same as Grade 3	Permanently discontinue PDR001

Table 6-9 Mandatory dose modification requirements and recommended clinical management guidelines for infusion reaction events and cytokine release syndrome

Infusion reaction (NCI-CTCAE v4.03)		
Grade	Recommended Adverse Event management guidelines	Mandatory Dose Modification requirements
Grade 1 Mild reaction; infusion interruption not indicated; intervention not indicated	Increase monitoring of vital signs as medically indicated until the patient is deemed medically stable in the opinion of the investigator.	Continue PRD001 treatment
Grade 2 Requires infusion interruption but responds promptly to symptomatic treatment (e.g., antihistamines, NSAIDS, narcotics, IV fluids); prophylactic medications indicated for ≤24 hrs	
 ● Stop Infusion ● Additional appropriate medical therapy may include but is not limited to: 
 ● IV fluids ● Antihistamines ● NSAIDS ● Acetaminophen ● Narcotics ● Increase monitoring of vital signs as medically indicated until the patient is deemed medically stable in the opinion of the investigator. ● If symptoms resolve within one hour of stopping drug infusion, the infusion may be restarted at 50% of the original infusion rate (e.g. from 100 mL/hr to 50 mL/hr). Otherwise dosing will be held until symptoms resolve and the patient should be re-premedicated for the next scheduled dose. ● Patient may be premedicated 1.5hr (± 30 minutes) prior to infusion of PDR001 with: 
 ● Diphenhydramine 50 mg po (or equivalent dose of antihistamine). ● Acetaminophen 500-1000 mg po (or equivalent dose of analgesic). 	1 st occurrence: Continue PRD001 treatment at the same dose and schedule with premedication 2 nd occurrence: Despite premedication or prolongation of infusion, consider permanent discontinuation of PDR001.
Grade 3: Prolonged (i.e., not rapidly responsive to symptomatic medication and/or brief interruption of infusion); recurrence of symptoms following initial improvement;	
 ● Stop Infusion ● Additional appropriate medical therapy may include but is not limited to: 
 ● IV fluids ● Antihistamines ● NSAIDS ● Acetaminophen ● Narcotics 	Permanently discontinue PDR001

Infusion reaction (NCI-CTCAE v4.03)		
Grade	Recommended Adverse Event management guidelines	Mandatory Dose Modification requirements
hospitalization indicated for other clinical sequelae (e.g., renal impairment, pulmonary infiltrates) Grade 4: Life-threatening; pressor or ventilatory support indicated	
 • Oxygen • Pressors • Corticosteroids • Epinephrine 
 • Increase monitoring of vital signs as medically indicated until the patient is deemed medically stable in the opinion of the investigator. Hospitalization may be indicated.	

Table 6-10 Mandatory dose modification requirements and recommended clinical management guidelines for “other” potential immune-related AEs of special interest

Other- Autoimmune neuropathy, demyelinating polyneuropathy, Guillain Barre, Myasthenia Gravis- like syndrome, Non-infectious myocarditis, pericarditis, pancreatitis, and Grade 3 Fatigue with rapid onset in absence of disease progression		
Grade	Recommended Adverse Event management guidelines	Mandatory Dose Modification requirements
Mild (Grade 1)	Provide symptomatic treatment	Continue PDR001 treatment
Moderate (Grade 2) or Grade 1 that does not improve with symptomatic treatment	
 • Provide symptomatic treatment • Systemic corticosteroids may be indicated • Consider biopsy for confirmation of diagnosis • A specialist should be consulted 	1 st occurrence: 
 • Interrupt PDR001 until recovery to ≤ Grade 1 or baseline. 
 • Once recovered, may restart PDR001 treatment at the same dose and schedule AE resolution to ≤ Grade 1 or baseline must occur within a period of 12 weeks since event has been identified, otherwise PDR001 must be permanently discontinued. 2 nd occurrence: Permanently discontinue PDR001
Severe (Grade 3)	
 • All management for moderate irAEs and • Initiate systemic corticosteroids (prednisone or equivalent) at a dose of 1-2 mg/kg QD 	1 st occurrence: 
 • Interrupt PDR001 until recovery to ≤ Grade 1 or baseline 
 • May restart PDR001 treatment at the same dose and schedule AE resolution to ≤ Grade 1 or baseline must occur within a maximum period of 12 weeks since a Grade 3 event has been identified, otherwise PDR001 must be permanently discontinued. 2 nd occurrence: Permanently discontinue PDR001
Grade 4	Refer to management of severe AEs	Permanently discontinue PDR001.

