6.3.1.2 Dose Modification requirements for potential immune-mediated adverse events

6.3.1.2.1 Identification of and management requirements for AEs of potential immune-mediated etiology (irAE)

Adverse events of special interest (AESI) include AEs of a potential immune-mediated etiology (irAE) that are associated with PDR001 treatment. An irAE may be experienced by patients treated with PDR001 due to its mechanism of action; it is predicted based on the reported prior experience with other immunotherapies that have a similar mechanism of action. Investigators

must be vigilant and must carefully identify AEs that may be suggestive of potential irAEs as their appearance may be sub-clinical and early diagnosis is critical for its adequate management and resolution.

irAEs are typically low grade and self-limited, often occurring after multiple doses, and most frequently involving the GI tract (diarrhea/colitis), skin (rashes), liver (hepatitis), lung (pneumonitis), kidneys (nephritis) and endocrine systems (a variety of endocrinopathies) and rarely CNS (encephalitis). Serological, immunological and histological assessments should be performed as deemed appropriate by the investigator, to verify the potential immune-related nature of the AE, and exclude a neoplastic, infectious or metabolic origin of the AE.

[figure not shown]
Severe grade or persistent lower grade irAEs typically require interrupting or permanently discontinuing treatment and administration of systemic steroids or other non-corticosteroid immunosuppressive medication when systemic steroids are not effective. Early recognition of irAEs and initiation of treatment are critical to reduce the risk of complications, since the majority of irAEs are reversible with the use of steroids and other immune suppressants.

Patients should be instructed to return to the study site as soon as possible (instead of waiting for their next scheduled visit) if they experience symptoms consistent with an irAE. Patients who experience a new or worsening irAE should be contacted and/or evaluated by the study site more frequently.

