Based on literature from compounds with similar mechanism of action of PDR001, instructions have been developed regarding how to identify, assess severity and manage irAEs that may occur in patients receiving PDR001. The dose modification requirements and AE management guidelines for the potential irAEs are provided in the following tables: diarrhea/colitis ([Table 6-2](#)), hepatitis (liver laboratory alterations) ([Table 6-3](#)), skin (rash) ([Table 6-4](#)), nephritis ([Table 6-5](#)), pneumonitis ([Table 6-6](#)), encephalitis ([Table 6-7](#)), endocrinopathies ([Table 6-8](#)), PDR001-infusion reaction & cytokine release syndrome ([Table 6-9](#)), and other potential immune-related AEs of special interest ([Table 6-10](#)). Any grade 4 irAE must result in permanent discontinuation of PDR001.

Under the category of OTHERS ([Table 6-11](#) and [Table 6-12](#)) are included several irAE of interest that must be managed specifically and for which not specific guidance are provided in the table below. OTHERS include (but is not restricted to) the following events: autoimmune neuropathy, demyelinating polyneuropathy, Guillain-Barre, myasthenia Gravis-like syndrome, non-infectious myocarditis, non-infectious pericarditis, pancreatitis and rapid onset of grade 3 fatigue in the absence of disease progression.

Patients receiving PDR001 may experience irAEs other than those listed in this document; therefore, all AEs of unknown etiology associated with drug exposure should be evaluated to determine if they are possibly immune-related. In cases where the specific irAEs are not listed in the tables below, the investigator should follow the dose modification requirements in [Section 6.3.1.3](#) which details the measures to be taken for suspected (they could be potentially immune-related or non-immune-related) AEs. Investigators are encouraged to contact the sponsor as needed to discuss cases that warrant separate discussion outside of the scope of the current instructions.

The dosing modification requirements are mandatory; however, the AE management guidelines are recommendations and can be modified according to local practices. The management of irAEs may include initiation of antibiotics for prophylaxis against opportunistic infections.

Table 6-2 Mandatory dose modification requirements and recommended clinical management guidelines for potential immune-related diarrhea/colitis

Diarrhea/Colitis (NCI-CTCAE v4.03)		

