6.3.1.2.2 Guidance for corticosteroids tapering for management of immune-related AEs

Reduce prednisone dose by 2.5- to 5.0-mg decrements every 3–7 days until physiologic dose (5 to 7.5 mg of prednisone per day) is reached. Consider to complete tapering over a period of at least 4 weeks. Slower tapering of corticosteroids therapy may be recommended if the adverse event is not showing improvement. Once corticosteroid tapering is achieved at a level of 10 mg of prednisone/day (or equivalent), treatment with PDR001 can be restarted as indicated in the dose modification tables.

6.3.1.3 Dose modification requirements for adverse events suspected to be related to study treatment

The required dose modification and management of adverse events that are considered to be related to study medication and do not have specific management requirements noted elsewhere in the protocol are provided in [Table 6-11](#) and [Table 6-12](#).

Table 6-11 Mandatory dose modification requirements and recommended clinical management guidelines for hematologic adverse events suspected to study treatment

Hematologic suspected AEs (NCI-CTCAE v4.03)		
Grade	Recommended Adverse Event management guidelines	Mandatory Dose Modification requirements
Neutropenia		
Grades 1, 2	NA	Continue PDR001 treatment
Grade 3, 4	Monitoring blood test more frequently (every 7 days for grade 3, and 3-5 days for grade 4)	
1st occurrence:
 
 Interrupt PDR001 until toxicity recovers to Grade ≤2 or baseline. 
 Once recovered restart PDR001 treatment at the same dose and schedule 
2nd occurrence:
 
 Interrupt PDR001 until toxicity recovers to Grade ≤2 or baseline 
 Once recovered restart PDR001 treatment at the same dose and schedule 
AE resolution to ≤ Grade 2 or baseline must occur within a maximum period of 12 weeks since Grade 3 or 4 event has been identified, otherwise PDR001 must be permanently discontinued
 
3rd occurrence: Permanently discontinue PDR001.

Febrile Neutropenia	Apply Institutional guidelines	Follow- neutropenia Grade 4 requirements (above)
Thrombocytopenia (NCI-CTCAE v4.03)		
Grade 1, 2, 3 without clinical significant bleeding	Grade 3: monitoring blood test more frequently (every 7 days)	Continue PDR001 treatment

Hematologic suspected AEs (NCI-CTCAE v4.03)		

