Grade	Recommended Adverse Event management guidelines	Mandatory Dose Modification requirements
Grade 3 with clinical significant bleeding OR Grade 4	Grade 3: monitoring blood test more frequently (every 3-5 days)	
1st occurrence:
 
 ● Interrupt PDR001 until toxicity resolves to Grade ≤ 2 or baseline. 
 ● Once recovered restart PDR001 treatment at the same dose and schedule 
2nd occurrence:
 
 ● Interrupt PDR001 until toxicity resolves to Grade ≤ 2 or baseline 
 ● Once recovered restart PDR001 treatment at the same dose and schedule 
AE resolution to \leq Grade 2 or baseline must occur within a maximum period of 12 weeks since Grade 3 with clinically significant bleeding or Grade 4 event has been identified, otherwise PDR001 must be permanently discontinued.
 
3rd occurrence: Permanently discontinue PDR001.

Table 6-12 Mandatory dose modification requirements and recommended clinical management guidelines for non-hematologic adverse events suspected related to study treatment

Non-Hematologic suspected AEs (except Grade 2 alopecia, Grade 2 fatigue) (NCI-CTCAE v4.03)		
Grade	Recommended Adverse Event management guidelines	Mandatory Dose Modification requirements
Grade 1-2 tolerable	
 ● Monitor closely ● Provide supportive care according to institutional standards 	Continue PDR001 treatment at the same dose and schedule
Grade 2 intolerable or Grade 3	
 ● Monitor closely ● Provide supportive care according to institutional standards 	
1st or 2nd occurrence:
 
 ● Interrupt PDR001 until toxicity recovers to Grade ≤ 1 or baseline. 
 ● Once recovered restart PDR001 treatment at the same dose and schedule 
AE resolution to Grade ≤ 1 or baseline must occur within a maximum period of 12 weeks since intolerable Grade 2 or Grade 3 event has been identified, otherwise PDR001 must be permanently discontinued.
 
3rd occurrence: Permanently discontinue PDR001

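### Section 6.3.1.2.1 stops PDR001 for any grade 4 irAE, yet sends unlisted irAEs to tables that direct or permit restart, with no precedence stated; its OTHERS paragraph also cites the wrong tables.

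*Protocol*

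**What the plan says.** Section 6.3.1.2.1 of the protocol defines irAEs by potential cause: "Adverse events of special interest (AESI) include AEs of a potential immune-mediated etiology (irAE) that are associated with PDR001 treatment". It then sets a rule without exceptions: "Any grade 4 irAE must result in permanent discontinuation of PDR001". It also calls the dose modification requirements mandatory, in contrast to the management advice beside them.

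Events outside the irAE tables are handed on: the investigator is told to apply the dose rules of Section 6.3.1.3 instead. Of that target the protocol adds: "which details the measures to be taken for suspected (they could be potentially immune-related or non-immune-related) AEs". Grade 4 is not reserved in that sentence.

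Section 6.3.1.3 consists of Tables 6-11 and 6-12. Its opening limits them to treatment-related events that "do not have specific management requirements noted elsewhere in the protocol".

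The OTHERS paragraph of Section 6.3.1.2.1 (Guillain-Barre, non-infectious myocarditis and similar events) cites Tables 6-11 and 6-12 and states that specific guidance is lacking. Just before it, the section's list of irAE tables cites Table 6-10 for the other immune-related events of special interest.

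**The concern.** An investigator with a grade 4 event that may be immune-mediated, and that no irAE table lists, meets two instructions in one section. One ends treatment. The other leads to tables under which treatment can resume. Both are dose rules, so neither can be set aside as advice.

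At stake is re-exposure after a life-threatening immune event. Section 6.3.1.1 allows no change of dose, so a restart is at the full 400 mg. Section 8.6 provides no data monitoring committee, and Section 12 allows no authorized deviations, so sites depend on the written rule. Enrollment has closed, but Section 6.1.5 lets patients continue PDR001 after 10-Aug-2018, so the text still governs treatment.

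**Working it through.** No formula applies; the check is to set the grade 4 instructions side by side.

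| Source | Instruction at grade 4 | Against the blanket rule |
|---|---|---|
| Section 6.3.1.2.1, blanket sentence | Permanent stop | – |
| Tables 6-2 to 6-10 (9 tables) | Permanent stop in every grade 4 row | Agrees |
| Table 6-11, neutropenia | Interrupt; restart after recovery at 1st and 2nd occurrence; stop at 3rd | Conflicts if the event is an irAE |
| Table 6-11, febrile neutropenia | Refers to the neutropenia row | Same conflict |
| Table 6-11, thrombocytopenia | As for neutropenia | Same conflict |
| Table 6-12, non-hematologic | Interrupt and consider stopping; restart if benefit-risk supports it; stop at 2nd occurrence | Stopping satisfies both |

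In Table 6-8 the grade 4 row concerns autoimmune diabetes; for other grade 4 endocrinopathies the blanket sentence does the work.

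**Table 6-11.** The restart rows clearly include grade 4. In the neutropenia row, recovery "must occur within a maximum period of 12 weeks since Grade 3 or 4 event has been identified"; in the thrombocytopenia row the clock runs "since Grade 3 with clinically significant bleeding or Grade 4 event has been identified". After recovery, restart is an instruction and not an option. An immune-mediated grade 4 thrombocytopenia, which no table from 6-2 to 6-10 lists, therefore receives opposite orders.

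**Table 6-12.** Restart depends on a benefit-risk judgement, and stopping is named as something to consider. A site that stops breaks neither rule. The defect is that the table offers a choice that the blanket sentence has already removed.

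**Overlap.** The two rules share events. An irAE is defined by potential immune cause, and the routing sentence says that Section 6.3.1.3 handles events that may be immune-related.

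**OTHERS.** The paragraph names eight events: autoimmune neuropathy, demyelinating polyneuropathy, Guillain-Barre, myasthenia gravis-like syndrome, myocarditis, pericarditis, pancreatitis and rapid-onset grade 3 fatigue. All eight are in the heading of Table 6-10, whose grade 4 row requires a permanent stop. Tables 6-11 and 6-12 name none of them.

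**Frequency.** The documents give no rate for unlisted grade 4 irAEs. Section 1.2.1.2 gives some indication for the cytopenias. The suspected grade 3/4 events listed for the first-in-human study (160 patients) include no neutropenia, febrile neutropenia or thrombocytopenia; nor do those listed for the nasopharyngeal study (32 patients). Taking the first list as complete, 0 of 160 gives a one-sided 95% upper limit of 1 − 0.05^(1/160) = 1.9%. Grades 3 and 4 are pooled there, and median exposure in the phase II part was only 8.0 weeks. The interim list for this study shows none of the three either, but it covers only the most common events.

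**The case against.** The best defence is that the text, read as a whole, already gives the answer. Section 6.3.1.3 covers only events without specific requirements elsewhere, and the blanket sentence can count as such a requirement. The restart rows keep a purpose, because they also serve events that are not immune-related. Other rules narrow the risk. Section 6.3.1.1 ends treatment if a suspected event has not recovered to grade 1 or baseline within 12 weeks, or if steroids for an irAE stay above 10 mg/day. Section 6.4.3 repeats a steroid limit before the next dose. Section 6.3.1.2.1 also encourages contact with the sponsor about cases outside its instructions.

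Much of this stands. The scope clause does point to the blanket rule, and the backstops catch patients who do not recover. But a one-line general rule is not plainly a specific management requirement, and unlisted irAEs reach Section 6.3.1.3 precisely because no table covers them. The backstops do not restate the grade 4 rule and do not catch a patient who recovers quickly. A site that has been given an express route has little reason to think that its case lies outside the instructions.

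The defence fully defeats one stronger reading. A reader might infer that the protocol allows restart after grade 4 Guillain-Barre or myocarditis. It does not: Table 6-10 names these events and stops treatment at grade 4, and the same section cites Table 6-10 correctly just before the faulty reference.

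**Conclusion.** The point holds as a minor safety-conduct correction, in two parts.

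- **Unlisted irAEs.** The blanket stop and the routing to Section 6.3.1.3 overlap with no stated precedence. The conflict is direct for grade 4 neutropenia, febrile neutropenia and thrombocytopenia classified as irAEs. For grade 4 non-hematologic irAEs the text is ambiguous but not contradictory.
- **OTHERS events.** The table reference is wrong and so is the remark about missing guidance, but Table 6-10 settles the rule.

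A reader might go further and conclude that every unlisted grade 4 irAE receives two incompatible orders. Table 6-12 does not support that, because its restart is optional.

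The reach is limited to patients still on PDR001 among the 116 enrolled; the documents do not say how many that is. No endpoint, sample size or analysis is affected. The conclusion assumes that the sponsor means the blanket sentence as written, which the nine irAE tables bear out. If hematologic irAEs were meant to be exempt, the defect is an unstated exception, and the same edit cures it.

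**What to change.** 1. In the OTHERS paragraph of Section 6.3.1.2.1, replace the reference to Tables 6-11 and 6-12 with Table 6-10, and delete the remark that specific guidance is not provided.
2. In Section 6.3.1.3 and in the grade 4 rows of Tables 6-11 and 6-12, add a sentence such as: *A grade 4 event that the investigator classifies as an irAE under Section 6.3.1.2.1 requires permanent discontinuation of PDR001, whatever this table says about restart.*
3. If any exception is intended, for example for hematologic events, list it beside the blanket rule.

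The test should be the investigator's classification under Section 6.3.1.2.1. Limiting restart to events judged not immune-related would bring in a standard that the protocol does not define, and it fits poorly with a definition based on potential immune cause. Read broadly, it could largely disable the restart rows of Table 6-11.

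The cost is a short written amendment under Section 12.1, with sponsor and IRB/IEC/REB approval, and health authority approval where required. That section lets a change needed for patient safety take effect before IRB/IEC/REB approval. Assessments, data collection and the SAP stay as they are.

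### The OTHERS paragraph in Protocol Section 6.3.1.2.1 cites Tables 6-11 and 6-12 for eight immune-related events whose mandatory dose rules are in Table 6-10 and are stricter at defined points

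*Protocol*

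**What the plan says.** Section 6.3.1.2.1 of the Protocol has three consecutive paragraphs that assign immune-related events (irAEs) to dose-modification tables.

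- The first assigns each organ category to a table. It sends infusion reactions to Table 6-9 "and other potential immune-related AEs of special interest" to Table 6-10, and ends with a general rule: "Any grade 4 irAE must result in permanent discontinuation of PDR001".
- The second, the OTHERS paragraph, refers its category to Tables 6-11 and 6-12 and says that there "are included several irAE of interest that must be managed specifically and for which not specific guidance are provided in the table below". It then names eight events: autoimmune neuropathy, demyelinating polyneuropathy, Guillain-Barré syndrome, a myasthenia-like syndrome, myocarditis and pericarditis of non-infectious origin, pancreatitis, and rapid-onset grade 3 fatigue without progression. It adds that the list is not exhaustive.
- The third sends irAEs that the tables do not list to Section 6.3.1.3, where Tables 6-11 and 6-12 sit.

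The heading row of Table 6-10 reads "Other- Autoimmune neuropathy, demyelinating polyneuropathy, Guillain Barre, Myasthenia Gravis- like syndrome, Non-infectious myocarditis, pericarditis, pancreatitis", and adds "Grade 3 Fatigue with rapid onset in absence of disease progression". Section 6.3.1.3 limits Tables 6-11 and 6-12 to related events that "do not have specific management requirements noted elsewhere in the protocol". Section 6.3.1.2.1 makes the dose-modification rules mandatory and the management guidance advisory.

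**The concern.** The OTHERS paragraph is the only narrative text that names these events, and it gives the wrong tables for them. Its two errors reinforce each other: it says the events have no specific guidance, and the next paragraph sends unlisted irAEs to the section that holds the tables it cites. A site reading only those two paragraphs gets an instruction that is coherent but wrong.

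What is at stake is dosing safety in a list that includes myocarditis, Guillain-Barré syndrome and a myasthenia-like syndrome. A site following Table 6-12 could keep dosing through a tolerable grade 2 event, or restart after a second event that should have ended treatment. It would also miss Table 6-10's advice on specialist consultation and its grade 3 corticosteroid guidance. No efficacy endpoint is involved.

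**Working it through.** No arithmetic beyond counting applies, so the check sets the texts side by side.

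**Events.** The OTHERS paragraph names eight, and the Table 6-10 heading carries the same eight. Fatigue is listed only at grade 3, so 8 − 1 = 7 events can fall in the grade 1–2 rows.

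**Which cited table would apply.** Table 6-11 covers hematologic events. None of the eight is hematologic, so a reader following the pointer ends at Table 6-12.

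**Rules compared.** The Table 6-10 row that triggers interruption below grade 3 is "Moderate (Grade 2) or Grade 1 that does not improve with symptomatic treatment". The Table 6-12 row for tolerable grade 1–2 is "Continue PDR001 treatment at the same dose and schedule".

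| Situation | Table 6-10 | Table 6-12 | Result |
|---|---|---|---|
| Grade 1, improving | continue | continue | same |
| Grade 1 not improving (tolerable), or tolerable grade 2, first occurrence | interrupt | continue | 6-10 stricter |
| Intolerable grade 2, first occurrence | interrupt | interrupt | same |
| Grade 1 not improving (tolerable), or tolerable grade 2, second occurrence | stop permanently | continue | 6-10 stricter |
| Intolerable grade 2, second occurrence | stop permanently | interrupt, restart on recovery; stop at third | 6-10 stricter |
| Grade 3, first occurrence | interrupt | interrupt | same |
| Grade 3, second occurrence | stop permanently | interrupt, restart on recovery; stop at third | 6-10 stricter |
| Grade 4 | stop permanently | first occurrence may restart | overridden by the grade 4 rule |

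The grade 1–2 rows apply to seven events and the grade 3 rows to all eight.

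**Other rules that might close the gap.**

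- Section 6.4.3 requires PDR001 to be discontinued if prednisone cannot be brought below 10 mg/day before the next dose, whichever table is used. It acts only when steroids are given. Table 6-10 says at grade 2 that they may be indicated; Table 6-12 mentions only supportive care.
- Section 6.3.1.2.1 says that persistent lower-grade irAEs typically lead to interruption or discontinuation. This describes usual practice and is not a mandatory rule.
- The 12-week recovery limit in Section 6.3.1.1 runs from the point at which a grade requires interruption. Under Table 6-12 a tolerable grade 2 event never reaches that point.
- None of these prevents restart after a second event that has recovered with steroids tapered.

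**The case against.** The strongest reply is that the Protocol resolves the slip itself. The preceding paragraph assigns the category to Table 6-10. The following paragraph sends only unlisted irAEs to Section 6.3.1.3, and these eight are listed. The heading of Table 6-10 names them, and the scope sentence of Section 6.3.1.3 excludes events with specific requirements elsewhere. Investigators are also encouraged to contact the sponsor about cases outside the instructions. To go wrong, a site would have to rely on the OTHERS paragraph and overlook the text around it. This stands: the intended table is clear, and the point is minor.

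It does not remove the point. The rules are mandatory, the wrong pointer is in current operative text, and following it gives a different dosing action.

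Three stronger readings are tempting but not supported:

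- A reader might infer that Table 6-10 is stricter throughout grades 1–2. It is not: improving grade 1 and a first intolerable grade 2 event are handled alike in both tables.
- A reader might infer that a grade 4 event could be rechallenged under Table 6-12. The general grade 4 rule in Section 6.3.1.2.1 requires discontinuation.
- A reader might infer that the Protocol leaves unlisted irAEs without a rule. It does not: the paragraph after OTHERS sends them to Section 6.3.1.3.

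**Conclusion.** The point holds as a wrong cross-reference, with an inaccurate clause attached, in a mandatory dose-safety section. Eight events are affected, and the two candidate tables differ in two respects:

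1. First occurrence of tolerable grade 2, or of tolerable grade 1 that does not improve (seven events): interruption under Table 6-10, continued dosing under Table 6-12.
2. Second occurrence of grade 2, non-improving grade 1 or grade 3 (fatigue at grade 3 only): permanent stop under Table 6-10; continued dosing, or interruption with restart, under Table 6-12.

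This takes non-improving grade 1 as tolerable, and reads a second occurrence as one at a grade on which Table 6-10 acts.

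The exposure is narrow. Amendment 3 closes enrollment, while Section 6.1.5 lets treatment continue after 10-Aug-2018. Only patients still on treatment, at sites relying on the OTHERS paragraph, could be affected. Their number is not given, and nothing in the documents shows that any patient was managed under the wrong table. Severity is minor, and the analysis of overall response rate is not touched.

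**What to change.** Make three edits to the OTHERS paragraph of Section 6.3.1.2.1:

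1. Replace the reference to Tables 6-11 and 6-12 with Table 6-10.
2. Delete the clause saying that no specific guidance is provided.
3. Delete the parenthetical that makes the list non-exhaustive.

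The third edit is needed because of the first. If the list stayed open-ended and pointed to Table 6-10, an unlisted irAE would fall under Table 6-10 by that paragraph and under Section 6.3.1.3 by the next. Myositis is an example: Section 1.2.1.2 reports a suspected grade 2 serious case in another PDR001 study, and neither the OTHERS paragraph nor Table 6-10 names it. With the parenthetical removed, such events stay under Section 6.3.1.3, as the Protocol already requires.

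The cost is three short text changes, with the usual amendment approval under Section 12.1. No intended dosing rule, data collection or analysis changes.
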